### **6.2 Treatment Study Period**

#### **Visit 1 (Day 1)**

Participants will have their first session with the study clinician at Visit 1. Prior to the session, study staff will meet with the participant to download their actigraphy. Study staff will provide the study clinician with the initial clock time at which each participant should take melatonin. The initial clock time of melatonin administration for participants assigned to the M-DLMO condition will be set at 3 h before their measured baseline DLMO. The initial clock time of melatonin administration for participants assigned to the E-DLMO condition will be set at 5 h before their average time of sleep onset at baseline per most recent 7 days of actigraphy. Participants be provided with a 14-day supply of melatonin 0.5 mgs, which they will begin taking that evening.

During the first visit, study staff will query whether participants have had any changes in their medications or medical history since the screening, and review concomitant medications. Participants' baseline sleep diary and actigraphy data will be reviewed by the study clinician. The study clinician will provide them with specific instructions regarding when to take melatonin, their bed time, their wake time, and when to dim ambient lighting and electronic devices to their lowest usable level (timed to be approximately 60 minutes before their scheduled bedtime). They will be provided with a handout summarizing this information.

#### **6.2.1 Follow-up (Weeks 1-4)**

Participants will continue to take melatonin 0.5 mg at the scheduled time daily for the 4 weeks of the study. At approximately Week 1, they will be provided with an additional 14-

day supply of melatonin. Each follow-up session (approximately Weeks 1-4) will follow an identical protocol:

1. Study staff will meet with the participant to query the following: review previously reported medications and current use of previously reported medications; any new medications; any side effects from the melatonin; any unexpected medical conditions since their last visit; any new medical diagnoses or changes in medical history since their last visit. They will also meet with the participant to download their actigraphy, TrackCap data, and complete a pill count. Compliance with melatonin administration timing per TrackCap, the pill count, changes in medical history or medications, and side effect information, will be provided to the study clinician. Only melatonin administration deviations  $\geq$  30 minutes will be considered non-compliant and be reported as protocol deviations.
2. During the follow-up treatment session, the study clinician will review side effects/adverse events, compliance with bed and wake times, adherence to melatonin administration time, and address any barriers to compliance. Participants will be instructed to advance the time of melatonin administration by 1 h and their bed-wake schedule by 1 h (without altering their total time in bed from their baseline average) at each weekly treatment session until they reach their desired bed-wake schedule. The study clinician may also choose to adjust the melatonin administration time or time in bed schedule using their discretion and clinical judgement as needed. At each follow-up session, participants will be provided with a handout summarizing the main components of the session.

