### **1.3 Hypothesis**

#### Specific Aims

Aim 1: Compare pre- to post-treatment changes in DLMO in M-DLMO vs. E-DLMO conditions.

Hypothesis 1: Participants in the M-DLMO condition will show greater improvements in DLMO (i.e., greater advance of DLMO) relative to participants in the E-DLMO condition after 4 weeks of exogenous melatonin.

Aim 2: Compare pre- to post-treatment changes in objective and subjective sleep parameters and daytime symptoms in M-DLMO vs. E-DLMO conditions.

Hypothesis 2: Participants in the M-DLMO condition will show greater improvements in objective (per wrist actigraphy) and subjective (per daily sleep-wake diary) sleep parameters (specifically, total sleep time, initial sleep latency, sleep onset time, sleep offset time) after 4 weeks of exogenous melatonin. They will also show greater improvements in daytime symptoms.

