## 5 STUDY TREATMENTS

### 5.1 Allocation to Treatment

Eligible participants will be randomized using the minimization method (Pocock et al. 1975) in a 1:1 ratio to M-DLMO or E-DLMO. Assignment to condition will be balanced by age and baseline sleep onset time on free days. For allocation of participants, a computer program (the Treatment Assignment System, created by UM's Consulting for Statistics, Computing, and Analytics Research) will be used by the study coordinator to generate the group assignment at enrollment for each participant.

Participants will be blinded to the specific study hypotheses and to their group assignment. The study clinician will be blinded to group assignment. The study coordinator, who communicates the time of melatonin administration to the study clinician, will not be blinded to the actual DLMO of participants in the M-DLMO condition; however, they will be blinded to the actual DLMO of participants in the E-DLMO condition until their participation is complete.

Due to individual variation in melatonin levels or errors in the saliva collection process, it is possible that DLMO will not be able to be determined for a small proportion of participants. To retain these participants in the protocol, if they are randomly assigned to the M-DLMO condition, the study coordinator may change their assignment to the E-DLMO condition. Data for these participants will be examined post-hoc upon completion of the study using sensitivity analyses before determining whether to retain or discard their data from analyses.

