## **9. DATA ANALYSIS/STATISTICAL METHODS**

### **9.1 Sample Size Determination**

We based our sample size estimation on the number of participants necessary to detect a 1 h change in DLMO; the sample size required to detect this change at 90% power with an alpha of 0.05 is 23 per group. Thus, our proposed sample of 25 participants per group (50 total) should be adequate to detect a clinically meaningful change in DLMO.

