#### ***9.2.1 Analysis of Primary Endpoint***

Change in DLMO from pre- to post-treatment will be calculated in minutes for each participant. A 2-tailed t-test will evaluate the difference between the change in DLMO between the two groups.

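### The advance pursued depends partly on each participant's distance from a personal desired schedule; leaving this pre-treatment quantity out of the primary DLMO analysis is an avoidable loss of precision of uncertain size

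*Combined protocol and SAP*

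**What the plan says.** Section 6.2.1 gives both arms the same rule. Dose time and bed-wake schedule move 1 h earlier "at each weekly treatment session until they reach their desired bed-wake schedule", with time in bed held at its baseline average. The study clinician may also depart from the rule on judgement.

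The Specific Aims count "greater improvements in DLMO (i.e., greater advance of DLMO" as the improvement sought. Section 9.2.1 tests it as follows: "A 2-tailed t-test will evaluate the difference between the change in DLMO between the two groups". No covariate is named there.

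On allocation, section 5.1 says: "Assignment to condition will be balanced by age and baseline sleep onset time on free days". The desired schedule is not a factor. Sections 6.1 and 6.2 and Table 1 do not list it as a recorded baseline item, although the clinician needs it to know when to stop advancing.

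Section 9.2 adds a general rule: baseline variables are compared between the arms, and those that look like confounders are then controlled for.

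**The concern.** A participant whose target is 1 h away gets one step. A participant 3 h away gets three. If DLMO follows the schedule even in part, some of the spread in DLMO change is set by a quantity known before treatment that has nothing to do with how the dose was timed. An unadjusted t-test puts that spread in the error term.

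The existing provisions do not recover it:

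- Balancing on free-day sleep onset helps comparability on one side of the distance. An unadjusted test gains no precision from that balance, and two participants with the same onset and age can have different targets.
- The section 9.2 rule selects on observed imbalance, not on prognostic strength. A strong but balanced predictor would stay in the error term, and a variable that is never recorded cannot be selected.

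At stake is precision in a trial of 25 per arm. The desired time as it stood before allocation may also be unrecoverable later if it is not written down prospectively.

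**Working it through.** **Inputs from the documents**

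- Section 9.1 sets a target of 1 h and states that "the sample size required to detect this change at 90% power with an alpha of 0.05 is 23 per group". Planned enrolment is 25 in each arm, 50 in all.
- Allocation 1:1 (section 5.1); two-sided test (section 9.2.1).
- Steps of 1 h at weekly sessions (section 6.2.1), at about Days 7, 14, 21 and 28 (Table 1).
- Treatment lasts 28 days (synopsis).

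**Not in the documents, so assumed**

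- The SD of DLMO change.
- The distribution of distance to the desired schedule.
- The slope, meaning hours of DLMO shift per hour of scheduled advance.

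**1. The plan's own figure.** Section 9.1 does not say whether its 1 h is a between-arm difference; I read it so, to match the test. With no SD stated, 23 per group cannot be reproduced independently, only back-solved. For a two-sided two-sample t-test, SDs of about 1.00 to 1.02 h give 23. An SD of 60 min requires 22.02, rounded up to 23. With 25 per arm and that SD:

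- power for 60 min is about 93%;
- the difference detectable at 90% power is 0.936 × 60 = 56.1 min.

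**2. How many steps can act.** The step assigned at Day 28 falls at the end of the 28-day treatment period and leaves little or no treated time to move DLMO. I therefore count three effective steps.

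**3. Spread of the advance pursued, two illustrations.**

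- One, two or three steps equally likely: variance = (1 + 0 + 1)/3 = 0.667 h², SD 0.82 h.
- Distance uniform over 2 to 6 h, capped at 3 h: 75% reach the cap. Mean = 0.25 × 2.5 + 0.75 × 3 = 2.875 h. Mean square = 0.25 × 6.333 + 0.75 × 9 = 8.333 h². Variance = 8.333 − 8.266 = 0.068 h², SD 0.26 h. The 2 to 6 h range is borrowed from the circadian delays reported in section 1.2, which are not distances to a desired schedule.

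**4. Share of variance explained.** With a total SD of 1 h, the share is slope² × variance.

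| Slope | Uniform 2 to 6 h, capped | 1 to 3 steps equally likely |
|---|---|---|
| 0.25 | 0.4% | 4.2% |
| 0.5 | 1.7% | 16.7% |
| 0.75 | 3.8% | 37.5% |

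**5. Effect of adjusting, slope 0.5.** Residual SD = 60 × √(1 − share).

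- Share 1.7%: SD 59.5 min; detectable difference 0.936 × 59.5 = 55.7 min.
- Share 16.7%: SD 54.8 min; detectable difference 0.936 × 54.8 = 51.3 min.

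**6. Chance imbalance.** Its standard error is 60 × slope × SD(steps) × √(2/25). At slope 0.5 and SD 0.82 h this is 6.9 min. The t-test's whole standard error is 60 × √(2/25) = 17.0 min. Since (6.9/17.0)² is about 0.17, this is the same 17% share again, not an added error.

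**The case against.** The strongest reply is that nothing here shows the trial to be underpowered. That stands. The SD implied by 23 per group may already contain this spread; if so, the unadjusted test detects 56 min, inside the 1 h target. A reader might infer that the schedule rule inflates the noise beyond what was planned. That would follow only if the planning SD omitted this source. In that case, with an SD of 1.023 h before the spread is added, unadjusted power at 25 per arm would be about 89.5% if distance explained 10% of the variance and 85.7% if it explained 20%. Section 9.1 states no SD, so the documents cannot settle which case applies.

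A reader might also infer that chance imbalance in required advance distorts the arm effect. It does not bias it: distance precedes allocation, and the imbalance is already part of the t-test's standard error, p-value and interval.

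Larger shares can be produced. Four equally likely steps at slope 0.5 give 0.25 × 1.25 = 31%. They depend on the Day 28 step moving DLMO, which the timetable hardly allows. Clinician discretion loosens the link between distance and steps further.

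It would also be too strong to say that distance is wholly unbalanced or that adjustment is ruled out. Free-day sleep onset is minimized on, and section 9.2 allows some adjustment. What remains is narrower: the desired time is unbalanced and not listed as recorded, and no covariate is pre-specified.

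For Aim 2, one might argue that clock times of sleep onset and offset largely follow the prescribed schedule in both arms. The plan analyses those outcomes with group-by-week models, and no loss has been quantified. Reporting distance from the desired schedule there is an optional extra.

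**Conclusion.** The point holds as an avoidable loss of precision. A pre-treatment quantity that partly determines the advance pursued is absent from the primary analysis, and the provisions in sections 5.1 and 9.2 do not replace it.

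Assuming a 60 min SD that includes this spread, three effective steps and a slope of 0.5, the share explained is about 2% to 17%, and the gain in detectable difference is between about 0.5 and 5 min. At a slope of 0.25 with most participants at the cap the gain is negligible; at 0.75 with steps evenly spread it would be larger. The documents do not say where the trial falls in this range. The case for acting rests on the low cost and on the need to record the desired time before allocation.

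**What to change.** 1. Record desired bed time and desired wake time for every participant before allocation.
2. Define required advance like for like: baseline mean bedtime minus desired bedtime, or the same for wake time, chosen in advance. Do not subtract desired bedtime from sleep onset; that would mix sleep latency into the measure. Cap it at the number of 1 h steps that can act before the post-treatment DLMO, which is three on the Table 1 timetable.
3. In section 9.2.1, replace the t-test with a pre-specified ANCOVA of DLMO change on arm, baseline DLMO, age, free-day sleep onset and required advance.
4. Do not use the realised advance as a covariate; it arises after randomization.
5. State the planning SD and its source in section 9.1.

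The cost is two CRF fields, SAP wording and four degrees of freedom: 50 − 2 = 48 for the t-test against 50 − 6 = 44 for the ANCOVA. At a given residual SD this raises the detectable difference by about 0.1 min. No visits or participants are added, and the schedule rule does not change.

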## **3 STUDY DESIGN**

### **Overview of research design**

This study is a randomized, controlled, parallel double-blind 4-week trial of 0.5 mg of exogenous melatonin (Emens et al. 2015) timed to either 3 h before actual DLMO based on in-home measurement (M-DLMO, n = 25) or 3 h before DLMO estimated at 2 h before average sleep onset time based on actigraphy and sleep diary (E-DLMO, n = 25). Note that the intervention tested is the method used to time melatonin administration--not melatonin per se, as all participants will receive the same dose of melatonin for the duration of the study.

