## 7.1 Primary Endpoint Assessments

Protocol activity and assessments are summarized in Table 1 above.

Primary endpoint: change in the time of DLMO from pre- to post-treatment.

To assess time of DLMO, all eligible participants (regardless of group assignment) will undergo in-home salivary DLMO collection at pre- and post-treatment, using the protocol established by [name] (Co-I) ([name] et al. 2015). Participants will be oriented to the collection procedures during their clinic visit. Participants will be in dim light starting 30 minutes prior to the first sample collection. Collection begins 6 hours prior to participants' habitual sleep onset per their most recent week of actigraphy at baseline. At post-treatment, collection begins 6 hours prior to participants' bed time as assigned at the final treatment session. Samples are collected via Salivette every 30 minutes until bedtime (13 samples total). They are provided with a kit, which includes: a checklist of procedures; a test tube rack; a toothbrush; a nightlight; blue-blocking Uvex glasses (with an Actiwatch attached to monitor compliance of use); an iPod programmed to alarm at collection times; a light medallion (an Actiwatch with light sensor worn around the neck to monitor compliance with light exposure); Salivette collection vials equipped with Track Cap, which will record when the vial was opened; and a label dispenser with pre-labeled labels. Participants wear the blue-blocking glasses throughout the dim light saliva collection and are required to remain seated in the 10 minutes before each sample. When the iPod alarms, participants brush their teeth without toothpaste, collect saliva by chewing on the Salivette, and deposit it in the vial. Participants are informed about the compliance measures utilized in the study. Samples will be stored in participants' freezers until they can be transported to our facility. Samples are centrifuged for two minutes, frozen, and assayed using Bühlmann Laboratory radioimmunoassay (ALPCO Diagnostics, Salem, NH) at **Solidphase Inc.** To ensure consistency and to minimize the effects of sleep schedule changes on the weekends/days off of work, whenever possible, all participants will complete DLMO collection on the third night of their typical workday sleep schedule (e.g., DLMO collection will occur on a Wednesday, Thursday, or Friday night for participants who work a traditional Monday-Friday schedule).

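### The weekly advance also applies at Follow-up 4, moving the post-treatment saliva window up to 1 h earlier for participants still short of their desired schedule

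*Combined protocol and SAP*

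**What the plan says.** Section 6.2.1 covers all four follow-up visits with one rule: "Each follow-up session (approximately Weeks 1-4) will follow an identical protocol". Under it, tablet time and bed-wake schedule each move 1 h earlier "at each weekly treatment session until they reach their desired bed-wake schedule". The clinician may depart from this "using their discretion and clinical judgement as needed". Nothing exempts the last visit, which Table 1 labels as Follow-up 4 (Final), nominal Day 28 ± 5 business days. Table 1 marks the post-treatment DLMO in the same column.

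Section 7.1 opens the post-treatment collection 6 h before the "bed time as assigned at the final treatment session". On frequency and end of sampling it says "Samples are collected via Salivette every 30 minutes until bedtime (13 samples total"). At baseline the window is anchored to habitual sleep onset from actigraphy, which is an observed quantity. Post-treatment it is anchored to a prescribed one.

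On dosing, Section 5.3.1 supplies two lots of 14 tablets, and Section 6.2 (Visit 1) says of the first lot: "which they will begin taking that evening".

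**The concern.** Sampling stops at the assigned bed time, so an onset that falls after that time is not seen. Any step taken at Follow-up 4 brings the stopping time forward before the primary endpoint is measured, while almost no treatment remains through which the new schedule could act on DLMO.

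The onsets lost this way are the late ones, in participants whose DLMO moved least. Section 9.2.1 calculates a change score for each participant, and the plan has no rule for a post-treatment DLMO that cannot be determined. Section 5.1 does foresee undeterminable DLMOs. Its remedy is to reassign M-DLMO participants to E-DLMO and examine their data in sensitivity analyses, which does not deal with an onset missed after treatment.

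**Working it through.** **Sampling window (plan's own figure).** 6 h × 60 / 30 min + 1 = 13 samples, which agrees with Section 7.1. With assigned bed time B, the window is [B − 6 h, B]. Moving B moves both ends equally.

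**Who steps at Follow-up 4, and by how much.** Let T be the number of hours by which the desired schedule precedes the Visit 1 schedule. Assume a full 1 h step at each of Follow-ups 1 to 3, and a last step no larger than is needed to reach the target. The Follow-up 4 step is then min(1, max(0, T − 3)) h:
- T = 3 h: 0 h
- T = 3.5 h: 0.5 h
- T = 4 h or more: 1 h

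In the last case the window runs from 10 h to 4 h before the Visit 1 bed time. Without the fourth step it runs from 9 h to 3 h before it.

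**Doses left.** 14 + 14 = 28 tablets from the evening of Day 1. With none missed, doses remaining at a session on Day D = max(0, 28 − D + 1). Day 28 leaves 1 and any later day leaves 0. Day 21, the earliest in-window date (5 business days before Day 28), leaves 8.

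**Advance needed for capture.** Let S be habitual sleep onset, p the hours by which baseline DLMO precedes S, d the hours by which the Visit 1 bed time precedes S, k the total hours stepped, and a the DLMO advance. Then B = S − d − k, and post-treatment DLMO is S − p − a. Onset falls before bed time only if a > k + d − p.

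The central value p = 2 h comes from Section 3, which doses the E-DLMO arm "3 h before DLMO estimated at 2 h before average sleep onset time". The range of 1 to 3 h for p is an assumption. So are the values of d, because Section 6.2 leaves the Visit 1 bed time to the clinician.

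| d (h) | p (h) | a must exceed, k = 3 | a must exceed, k = 4 |
|---|---|---|---|
| 0 | 1 | 2 h | 3 h |
| 0 | 2 | 1 h | 2 h |
| 0 | 3 | 0 h | 1 h |
| 0.5 | 1 | 2.5 h | 3.5 h |
| 0.5 | 2 | 1.5 h | 2.5 h |
| 0.5 | 3 | 0.5 h | 1.5 h |

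The threshold rises by the size of the Follow-up 4 step, whatever p and d are: 1 h for a full step, 0.5 h when T = 3.5 h.

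**Would keeping the later window lose early onsets instead?** With k = 3, onset precedes the first sample only if a > 6 + 3 + d − p. With d = 0 and p = 2 that is an advance of more than 7 h, so it is not a practical risk.

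**Interval from session to collection.** This is not fixed. Section 7.1 prefers, whenever possible, collection "on the third night of their typical workday sleep schedule", and gives Wednesday to Friday for a Monday-to-Friday worker. If same-evening collection is possible, the first such night is 2 nights after a Monday session, 1 after a Tuesday session and 0 after a Wednesday-to-Friday session. Collection could be later.

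**The case against.** **Order of events.** The plan does not state that collection follows the final session. If it came first, the bed time in force would already be that of Follow-up 3. This is a real ambiguity, but a window defined by a bed time assigned at the final session, together with Table 1's label for Follow-up 4, points strongly to session first and collection second.

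**The step is a default.** It stops once the target is reached, and the clinician may hold it back. Both limits stand: the step is at most 1 h and some participants will not take it. But discretion permits skipping the step without requiring it, so the endpoint's sampling window is left to individual choice.

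**The bedtime cut-off is the root cause.** This is correct. The Follow-up 4 step only tightens it, and sampling past the assigned bed time would address the cause more directly. That does not remove the case for dropping an avoidable tightening.

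**Stronger readings a reader might infer.** One is that every participant's window moves by a full hour. The documents do not support this: participants at target after three steps are unaffected, and a full hour needs a target at least 4 h before the Visit 1 schedule. Another is that the treatment comparison is biased. The rule is the same in both arms. If E-DLMO participants advance less, as Hypothesis 1 predicts, more of them might be lost, but that is conditional and cannot be sized from the documents. Nor does the gap between 25 planned and 23 required per group (25 − 23 = 2) show a loss of power, because there is no estimate of how many onsets would be missed.

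**Conclusion.** The point holds within limits. As written, Section 6.2.1 applies the advance at Follow-up 4, and Section 7.1 ties the primary-endpoint window to the bed time set there. For participants with a target more than 3 h before the Visit 1 schedule, the window moves up to 1 h earlier, with about one dose left on nominal Day 28. The DLMO advance needed for capture rises by the same amount, which makes a missing primary endpoint more likely in those who advanced least.

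This rests on three assumptions: collection follows the session, full steps were taken at the first three follow-ups, and the clinician does not withhold the fourth. The size of the shift does not depend on the assumed DLMO interval or starting bed time, but the thresholds themselves do. The number of participants affected and the effect on the treatment comparison cannot be computed from the documents. The change is worth making because it is cheap and protects the primary endpoint, not because a bias has been demonstrated.

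**What to change.** Amend Section 6.2.1 so that no advance of melatonin time or bed-wake schedule takes effect at Follow-up 4 until the post-treatment DLMO collection is done. Amend Section 7.1 to anchor that collection to the bed time in force from Follow-up 3, and to state that it is not affected by any schedule discussed at Follow-up 4. Any further advance starts after collection, through a line added to the handout already given at that session.

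The cost is a sentence or two in each section and one handout line, with no extra visit. There are two downsides. Participants with furthest to go get at most three in-study steps. The bedtime cut-off also remains, so onsets can still be lost in participants with little advance: with DLMO 2 h before sleep onset and the starting bed time at sleep onset, those who advanced 1 h or less after three steps.
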